### 7.3. Adverse Events

An AE is any untoward medical occurrence in a patient administered a pharmaceutical product, regardless of whether it has a causal relationship with this treatment.

For AE recorded in this study, the study period is defined for each patient as the time period from signature of the ICF through the end of the follow-up period (the day 57 [ $\pm 3$ ] follow-up visit or when a patient is confirmed as lost to follow-up). Any AE occurring on or after the first application of study drug is considered a treatment-emergent adverse event (TEAE). Unless there is a clear evidence that the onset date of an AE is prior to the first dose date, AEs with missing or partial onset dates will be classified as TEAEs as the conservative approach. All AE summaries will be conducted for TEAEs with the exception of serious adverse event (SAE) related summaries.

All AEs will be coded using the Medical Dictionary for Regulatory Activities (MedDRA version 17.1). The incidence of AEs will be summarized using descriptive statistics by system organ class (SOC) and preferred term.

Summaries will be presented for all AEs (overall, by severity and by causality), AEs determined by the investigator to be related to study treatment (ie, reasonable possibility; defined as related or with missing relationship), AEs determined by the investigator to be related to study treatment by severity, serious adverse event (SAEs), and AEs causing withdrawal from study. Summaries will be presented by treatment group and for all patients.

Each patient will be counted only once in each preferred term or SOC category for the analyses of safety. For the summaries by severity, patients are counted at the greatest severity. AEs with missing severity will be considered severe.

In addition, time to the first objective application site irritation, which is defined as the number of days between first dose date and the start of first objective application site irritation, will be analyzed using Kaplan-Meier methods by treatment group. The objective application site irritation is defined by AEs with preferred terms of 'Application site erythema', 'Application site exfoliation', 'Application site oedema', 'Application site papules' and 'Application site rash'. Those who did not experience objective application site irritation will be censored at last dose date.

Patient listings of SAEs and AEs leading to withdrawal from treatment will be presented.

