1.4. Known and Potential Risks and Benefits to Human Subjects

1.4.1. Risks of TV-45070

Following topical administration, no observed CNS adverse events were considered related to TV-45070 treatment by the investigator. Similarly, with the exception of 1 case of worsening coronary artery disease assessed as unrelated to study drug treatment, no significant ECG findings or cardiac arrhythmias were observed in studies of topical TV-45070.

In nonclinical dermal toxicology studies performed in minipigs, skin irritation was seen frequently in animals dosed either with TV-45070 or vehicle ointment, most often within the first week of dosing. The skin reactions are predominantly erythema and appear to be due to the ointment vehicle itself. In prior clinical studies, however, local reactions at the site of topical application of TV-45070 or matching placebo were seen infrequently. These reactions usually consisted of erythema or skin dryness with scaling of skin, were generally mild to moderate, and were approximately the same in frequency and severity for patients treated with either TV-45070 or placebo. Although the skin reactions may appear within a couple of days of exposure, they more often occur after a delay of 2 to 3 weeks and resolve soon after cessation of dosing. Worsening skin reactions should be monitored closely.

Due to low systemic exposure following topical administration of TV-45070 in humans, the DDI risk due to effects on CYP450 enzymes is thought to be low following topical administration. In vitro data using human liver microsomes have shown that TV-45070 is an inhibitor of several CYP450 enzymes. However, the compound is also highly bound to constituents in human plasma, so distribution into hepatocytes may be hindered, reducing the inhibition potential. In

vitro data using human cryopreserved hepatocytes have also shown that TV-45070 metabolite (M3) is an inhibitor of CYP3A4 and CYP2C19, which indicates a potential DDI risk between TV-45070 and medications that are primarily metabolized by CYP3A4 or CYP2C19. However, the preliminary results of a clinical study designed to assess the risk of these DDIs revealed no significant risk of an interaction.

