At the randomization visit (visit 3, day 1), eligible patients will be randomly assigned via interactive response technology (IRT) in a 1:1:1 fashion to 1 of 3 treatment groups: 4% w/w TV-45070 ointment, 8% w/w TV-45070 ointment, or placebo ointment. Randomization will be stratified by test results of the pharmacogenomic sample collected at the screening visit (homozygous minor allele [positive, AA], heterozygous [positive, AG], and homozygous common allele [negative, GG]) for R1150W polymorphism in the *SCN9A* gene. The patient will be instructed on how to apply the study drug. Under study site staff supervision, the area affected by PHN pain will be carefully defined by mapping the area of pain, and dosing will be prescribed to fully cover the affected area.

Efficacy assessments of pain NRS, NPSI, NePIQoL, and DSIS scores will be conducted at visit 3 (day 1) to establish baseline measurements. The site staff will apply the first dose of blinded study drug and the patient will record the date/time in the eDiary. Subsequent study drug applications will be performed by the patient at home. (If the affected area is not within reach of application by the patient [such as the posterior thoracic region], the patient's designated caregiver will apply the ointment, but the patient will record the time of application in the eDiary.)

During the 4-week treatment period, patients will apply double-blind study drug to the area of PHN pain twice daily in the morning (0700 ± 2 hours) and again in the evening (1900 ± 2 hours). The first dose of study drug will be applied at the clinic on day 1 (visit 3). Regardless of the clock time of the first dose application at visit 3, the evening dose for day 1 should be applied at 1900 ± 2 hours. The last dose of study drug will be applied at home on the evening of day 28, which is the day before visit 5. In the event that the patient cannot keep the scheduled appointment on day 29, it is nevertheless important for the patient to stop dosing on the evening of day 28. The morning and evening drug applications will be done after recording the response for the NRS pain score. At the start of the baseline pain assessment interval when the eDiary is provided, the eDiary will be used to record the NRS responses, PHN rescue medication use, and then, after randomization, the dates/times of study drug administration.

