3.11.3.1. Daily Routine

During this treatment period (and after the morning study drug application at the clinic on day 1), patients will self-administer topical study drug (4% or 8% w/w TV-45070 ointment or placebo ointment) according to the instructions provided by the study site. Study drug will be applied twice daily (in the morning [0700 ± 2 hours] and again in the evening [1900 ± 2 hours]). The first dose of study drug will be applied at the clinic on day 1 during the randomization visit. Regardless of the clock time of the first dose application at the randomization visit, the evening dose for day 1 should be applied at 1900 ± 2 hours. The last dose of study drug will be applied at home on the evening of day 28. No study drug will be applied on day 29, the day of visit 5 (week 4).

Patients who participate in the study in compliance with the protocol from the screening visit through the week 4 visit (visit 5, day 29) will be considered to have completed the study for statistical purposes.

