#### **4.5. Study Days and Visit Windows**

For both safety and efficacy by-visit summaries, the assessments at the scheduled visits will be summarized in the tables while all of the assessments including unscheduled visits will be listed. For patients who withdraw from the study, data at the early termination visit will be included in the last visit summaries. The last visit is defined as last observed postbaseline data up to Week 4 visit.

If there are multiple assessments at a scheduled postbaseline visit then the last non-missing value at that visit will be used for the by visit summary.

Study days will be numbered relative to the first day of study drug administration. The start of treatment (day 1) is defined as the date on which a patient applies the first dose of study drug, as recorded on the study drug diary. Days will be numbered relative to study start (ie, ..., -2, -1, 1, 2, ...; with day 1 being the start of study drug and day -1 being the day before the start of study drug).

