15.3.10	Serum Chemistry Laboratory Tests Results and Changes From Baseline to Each Visit by Treatment Group	Safety Analysis Set
15.3.11	Hematology Laboratory Tests Results and Changes From Baseline to Each Visit by Treatment Group	Safety Analysis Set
15.3.12	Urinalysis Laboratory Tests Results and Changes From Baseline to Each Visit by Treatment Group	Safety Analysis Set
15.3.13	Serum Chemistry Laboratory Tests Results Shifts From Baseline to Each Visit by Treatment Group	Safety Analysis Set

Summary number	Title	Population
15.3.14	Hematology Laboratory Tests Results Shifts From Baseline to Each Visit by Treatment Group	Safety Analysis Set
15.3.15	Urinalysis Laboratory Tests Results Shifts From Baseline to Each Visit by Treatment Group	Safety Analysis Set
15.3.16	Serum Chemistry Laboratory Tests Potentially Clinically Significant Abnormal Results by Treatment Group	Safety Analysis Set
15.3.17	Hematology Laboratory Tests Potentially Clinically Significant Abnormal Results by Treatment Group	Safety Analysis Set
15.3.18	Urinalysis Laboratory Tests Potentially Clinically Significant Abnormal Results by Treatment Group	Safety Analysis Set
15.3.19	Vital Signs Values and Changes From Baseline to Each Visit by Treatment Group	Safety Analysis Set
15.3.20	Vital Signs Potentially Clinically Significant Abnormal Values by Treatment Group	Safety Analysis Set
15.3.21	Electrocardiogram Findings Shifts From Baseline to Overall and Each Visit by Treatment Group	Safety Analysis Set
15.3.22	Electrocardiogram Variables Results and Changes From Baseline to Each Visit by Treatment Group	Safety Analysis Set
15.3.23	Dermal Irritation Finding at Each Visit by Treatment Group	Safety Analysis Set
15.3.24	Summary of Time (days) to First Application Site Skin Irritation by Treatment Group	Safety Analysis Set
15.3.25	Concomitant Medications by Therapeutic Class and Treatment Group	Safety Analysis Set

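### SAP 7.3 counts skin-irritation events through follow-up but censors event-free patients at last dose, so one event after day 28 can drive an arm's Kaplan-Meier incidence to 100%

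*SAP*

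**What the plan says.** SAP 7.3 defines objective application site irritation by five adverse event preferred terms. Time to event is the number of days from the first dose date to the start of the first such event, analysed by Kaplan-Meier within treatment group. The parts of the rule are as follows.

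- **Which events count.** Adverse event summaries other than those of serious events use treatment-emergent events, and "Any AE occurring on or after the first application of study drug is considered a treatment-emergent adverse event (TEAE". No end date is attached. Adverse events are recorded over "the time period from signature of the ICF through the end of the follow-up period", that is, to the day 57 (±3) visit.
- **When event-free patients leave.** "Those who did not experience objective application site irritation will be censored at last dose date".
- **When last dose falls.** Protocol 3.1 says that if the day 29 appointment cannot be kept, "it is nevertheless important for the patient to stop dosing on the evening of day 28". Protocol 3.11.3.1 likewise has no application on day 29.
- **Where it is reported.** SAP 12.1, Table 15.3.24: "Summary of Time (days) to First Application Site Skin Irritation by Treatment Group".

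The only nearby text with a week 4 limit is in SAP 4.1 and 4.5: "The last visit is defined as last observed postbaseline data up to Week 4 visit". It fixes which value enters a last-visit summary and does not cut off adverse event onset dates.

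**The concern.** The product-limit estimator needs the risk set at each time to be everyone still under observation for the event. Here a patient's stay in the risk set depends on the outcome. A patient who will have an irritation event on, say, day 35 is kept until day 35. A patient watched just as long without an event is removed at day 28. After the last censoring date in an arm, every patient left is a future event, so the survival estimate falls to zero at the last of those events.

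The curve up to day 28 is little affected. Patients who stop early meet a milder form of the same mismatch: their events after stopping count, while event-free early stoppers are removed at last dose. The serious damage is in the tail, the final incidence and the late quantiles, including the median. An arm with one late event could show an incidence of 100% and an estimable median, while an arm without one shows a low incidence and no median. That contrast would come from one onset date and not from the ointment.

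**Working it through.** The documents give no Kaplan-Meier or irritation-rate figure to reproduce. The arm size of 110 is from SAP 2.3, last dose on day 28 is from the protocol, and the end of follow-up is day 57. The event counts below are assumptions for illustration.

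**Formula.** S(t) = ∏(1 − d/n) over event days up to t, where d is events and n is patients at risk. Incidence is 1 − S(t).

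**Base case.** N = 110, no dropout. First events fall on days 5, 9, 12, 15, 16, 18, 20, 21, 23 and 25, and two more on day 29.

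- To day 25 there is no censoring, so S = 100/110 = 0.909 and incidence is 9.1%.
- As written, the 98 event-free patients are censored on day 28. On day 29, n = 2 and d = 2, so S = 0.909 × (1 − 2/2) = 0 and incidence is **100%**. The median is then 28 days after first dose.
- Event-free patients censored at day 57: on day 29, n = 100 and d = 2, so S = 0.909 × 98/100 = 0.891 and incidence is **10.9%**, median not reached. This equals the crude 12/110.
- Events counted only to last dose: **9.1%**. To last dose plus 1 day, with censoring at the same limit: **10.9%**.

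**Variations.**

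| Assumed situation | As written |
|---|---|
| One day 29 event instead of two | 100% (1 of 1 at risk) |
| A late event is the arm's only event (crude 1/110 = 0.9%) | 100% |
| 20 event-free early stoppers spread over days 3 to 27, two day 29 events | 10.1%, then 100% (12.4% if the other event-free patients are censored at day 57) |
| Two day 29 events, one event-free patient with a day 29 dose | 1 − 0.909 × 1/3 = 69.7% |

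Moving one late event to day 35 and varying the on-treatment count over 0, 2, 5, 10, 20 and 30 of 110 gives 100% every time as written. Censoring at day 57 gives 0.9% to 28.2%.

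**How often a late event might occur.** If a proportion p of patients have a first event after day 28, the chance of at least one among n patients is 1 − (1 − p)^n. No value of p is given, so the range is wide and assumed:

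| p | One arm (n = 110) | Any of three arms (n = 330) |
|---|---|---|
| 0.025% | 3% | 8% |
| 0.05% | 5% | 15% |
| 0.1% | 10% | 28% |
| 0.25% | 24% | 56% |
| 0.5% | 42% | 81% |
| 1% | 67% | 96% |
| 2% | 89% | 99.9% |

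**The case against.** Four points can be made for leaving the rule alone.

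*Late onsets should be rare.* Protocol 1.4.1 calls local reactions infrequent in earlier clinical studies and says "they more often occur after a delay of 2 to 3 weeks and resolve soon after cessation of dosing". This stands as a limit on likelihood, and it is why the table above extends down to 0.025%. It does not exclude late events. The skin is examined on day 29, after the last dose, and again at the follow-up visit. A reaction first noted and dated on day 29 is enough.

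*The 100% is fragile.* Last dose comes from eDiary entries, and patients keep the eDiary until visit 5. With one day 29 event and 1, 3, 5 or 10 event-free patients recording a day 29 dose, the final value is 54.5%, 31.8%, 24.2% or 17.4%. This also stands. From three such patients upward the false median disappears, but every value is still well above the crude 11/110 = 10.0%, and the cases all require dosing outside the protocol.

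*The SAP does not say which statistics Table 15.3.24 will show*, and its graph list has no visible irritation curve. That is true, so a printed final incidence is inferred. Quantiles from the same estimate would still be distorted.

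*The analysis is descriptive.* Crude incidence, dermal irritation by visit and the adverse event listings are planned separately, and an alert reader could spot the artefact. This limits the harm but does not make the estimate valid. Censoring at last dose may signal an intended on-treatment analysis, but the matching limit on events is not written.

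**Conclusion.** The concern holds. As written, the event window and the censoring date in SAP 7.3 do not match, and no other text in the protocol or SAP aligns them. If an event in an arm falls after the last dose of every event-free patient, that arm's Kaplan-Meier incidence ends at 100% whatever the true rate. In the illustrative arm this is 100% against 10.9%.

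The mechanism is certain. The 9.1% and 10.9% depend on the assumed counts, the 100% depends on all event-free patients stopping by day 28, and the likelihood depends on a late-onset rate that the documents do not give. No hypothesis test, efficacy result or sample size is affected. What is at risk is the planned time-to-event summary of local skin tolerability, which could suggest a difference between arms that does not exist. It should be corrected before unblinding, because a repair made afterwards would be post hoc.

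**What to change.** Amend the sentence in SAP 7.3 so that events and censoring share one window. Either rule works.

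- **(a) On-treatment.** Count only events with onset up to last dose, or up to last dose plus a stated lag, and censor all other patients at that same limit. A lag of at least 1 day keeps reactions first seen at the day 29 visit.
- **(b) Whole follow-up.** Keep all treatment-emergent events and censor event-free patients at their last adverse event assessment (visit 6, early termination visit or last contact). This adds about four weeks off drug to the time at risk, which a footnote to Table 15.3.24 should state.

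The SAP should also name the statistics that Table 15.3.24 will show. The cost is one or two sentences in the SAP, with no new data and no change to conduct.

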#### 7.4. Deaths

If any patient dies during the study all relevant information will be discussed in the patient's narratives included in CSR.

#### 7.5. Clinical Laboratory Tests

Summary statistics for chemistry, hematology, and urinalysis laboratory tests will be presented at baseline, week 2, week 4, last visit, and follow-up. Laboratory tests results and changes from baseline to each visit and last visit will be summarized using descriptive statistics. Shifts (below, within, and above the normal range) from baseline to each visit and last visit will be summarized using patient counts. The incidence of potentially clinically significant abnormal results will be summarized for laboratory data using descriptive statistics with the criteria specified in [Table 3](#).

**Table 3: Criteria for Potentially Clinically Significant Abnormal Laboratory Values**

Test	Criterion value
Serum chemistry	
Alanine aminotransferase (ALT)	$\geq 3 \times$ ULN
Aspartate aminotransferase (AST)	$\geq 3 \times$ ULN
Alkaline phosphatase	$\geq 3 \times$ ULN
Gamma-glutamyl transpeptidase (GGT)	$\geq 3 \times$ ULN
Lactate dehydrogenase (LDH)	$\geq 3 \times$ ULN
Blood urea nitrogen (BUN)	$\geq 10.71$ mmol/L
Creatinine	$\geq 177$ $\mu$ mol/L
Uric acid	
Men	$\geq 625$ $\mu$ mol/L
Women	$\geq 506$ $\mu$ mol/L
Bilirubin (total)	$\geq 34.2$ $\mu$ mol/L
Hematology	
Hematocrit	
Men	$< 0.37$ L/L
Women	$< 0.32$ L/L
Hemoglobin	
Men	$\leq 115$ g/L

Test	Criterion value
Women	$\leq 95$ g/L
White blood cell (WBC) counts	$\leq 3 \times 10^9$ /L $\geq 20 \times 10^9$ /L
Eosinophils	$\geq 10\%$
Absolute neutrophil counts (ANC)	$\leq 1 \times 10^9$ /L
Platelet counts	$\leq 75 \times 10^9$ /L $\geq 700 \times 10^9$ /L
Urinalysis	
Blood (HGB)	$\geq 2$ unit increase from baseline
Glucose	$\geq 2$ unit increase from baseline
Ketones	$\geq 2$ unit increase from baseline
Total protein	$\geq 2$ unit increase from baseline

ULN=upper limit of normal range.

Listings for potentially clinically significant abnormal laboratory data will be presented.

## 7.6. Vital Signs

Summary statistics for vital signs will be presented at baseline, weeks 2, 4, last visit, and follow-up. Vital signs values and changes from baseline to each visit and last visit will be summarized using descriptive statistics. The incidence of potentially clinically significant abnormal values will be summarized for selected vital signs using descriptive statistics.

**Table 4** specifies the criteria for identifying vital signs as potentially clinically significant abnormal. Note that in order to be identified as potentially clinically significant abnormal, a value would need to meet both conditions below: ie, have a value beyond the criterion value and a change of at least the magnitude specified in the change from baseline column.

**Table 4: Criteria for Potentially Clinically Significant Vital Signs**

Vital Sign	Criterion value	Change relative to baseline
Pulse	$\geq 120$ bpm	Increase of $\geq 15$
	$\leq 50$ bpm	Decrease of $\geq 15$
Systolic blood pressure	$\geq 180$ mm Hg	Increase of $\geq 20$
	$\leq 90$ mm Hg	Decrease of $\geq 20$
Diastolic blood pressure	$\geq 105$ mm Hg	Increase of $\geq 15$
	$\leq 50$ mm Hg	Decrease of $\geq 15$
Body temperature	$\geq 38.3^{\circ}\text{C}$	Change of $\geq 1.1^{\circ}\text{C}$

A listing for potentially clinically significant abnormal vital signs will be presented.

## 7.7. **Electrocardiography**

Shifts (normal and abnormal) from baseline to overall, weeks 2, 4, last visit, and follow-up will be summarized using patient counts. For overall, the worst postbaseline finding (the abnormal finding if there are both normal and abnormal findings) for the patient will be summarized. Summary statistics for electrocardiogram variables will be presented at baseline, each visit, and last visit. Electrocardiogram variables results and changes from baseline to each visit and last visit will be summarized using descriptive statistics.

## 7.8. **Physical Examinations**

Physical examinations, including height (to be obtained at the screening visit only) and weight will be performed at screening, baseline, week 2, week 4, follow-up, and early termination. Any physical examination finding that is judged by the investigator as a clinically significant change (worsening) compared to a baseline value will be considered an adverse event and reported as such.

## 7.9. **Dermal Irritation Findings**

Dermal irritation will be evaluated at baseline, week 2, week 4, follow-up, and early termination using the scale below:

- 0 = no evidence of irritation
- 1 = minimal erythema (barely perceptible)
- 2 = definite erythema, readily visible; minimal edema or minimal popular response
- 3 = erythema and papules
- 4 = definite edema
- 5 = erythema, edema, and papules
- 6 = vesicular eruption
- 7 = strong reaction spreading beyond test site

The frequency and percentage of patients falling into each scale at each visit and last visit will be descriptively summarized in the table.

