3.11.3.4. Early Termination Visit

For patients who discontinue the study drug prematurely (do not complete the per protocol treatment period), there will be an ET visit as soon as possible after the last study drug administration. General procedures for patients who withdraw prematurely from the study are described in Section 4.3.

The follow-up visit activities (Section 3.11.4.2) plus eDiary and unused study drug/rescue medication collection (and compliance checks) will be conducted at the ET visit, for ET visits occurring prior to visit 5 (day 29, week 4). (An ET visit may also occur after visit 5 but before the day that visit 6 would normally be scheduled, on day 57 ± 3 .) If adverse events or other safety findings are present at the ET visit, the clinical course of each adverse event will be monitored at suitable intervals until resolved or stabilized or returned to baseline, until the patient is referred to the care of a health care professional, or until a determination of a cause unrelated to the study drug or study procedure is made. Otherwise, the ET visit will be the last study visit for these patients.

Because premature discontinuations of treatment may occur at any time between randomization and the week 4 visit (visit 5, day 29), patients will be permitted to proceed directly from either visit 3 (day 1, randomization), visit 4 (day 15 ± 1 , week 2), or visit 5 (day 29, week 4) to the ET visit. For example, a patient who discontinues study drug on day 20 will have visit 4 (day 15 ± 1 , week 2) followed by visit 6 (ET) as soon as possible after day 20 with no visit 5 (day 29, week 4) in between.

The following procedures/assessments will be performed at the ET visit:

- perform adverse event inquiry
- review prior/concomitant medications

- review and record rescue medication use (if any) as concomitant medication, not using eDiary
- perform clinical laboratory tests (serum chemistry, hematology, and urinalysis)
- perform vital signs measurements
- perform physical examination (including body weight)
- perform 12-lead ECG (all ECGs taken in triplicate tracings obtained at least 1 minute apart [with an upper limit of 5 minutes apart])
- obtain urine pregnancy test (women of child-bearing potential only)
- obtain NPSI, DSIS, NePIQoL, and PGIC assessments
- evaluate area of PHN pain for dermal irritation
- measure maximal intensity of brush-evoked allodynia and maximal intensity of punctate-evoked hyperalgesia

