An ET visit should be conducted within 2 weeks after the last study drug administration. The activities for the ET visit are described in Section 3.11.3.4. Because premature discontinuations of treatment may occur at any time between randomization and the week 4 visit (visit 5, day 29), patients will be permitted to proceed directly from either visit 3 (day 1, randomization) or visit 4 (day 15 ±1, week 2) to the ET visit. For example, a patient who discontinues study drug on day 20 will have visit 4 (day 15 ±1, week 2) followed by visit 6 (ET) within 2 weeks after day 20 with no visit 5 (day 29, week 4) in between.

Data from any efficacy evaluations performed after the specified time will not be collected on the CRF; in the event, however, if such data are collected, these data will not be analyzed.

Patients with ongoing adverse events or clinically significant abnormal laboratory test results (as interpreted by the investigator) will be monitored as described in Section 7.1.2 and Section 7.3, respectively.

A patient who is randomly assigned to treatment (enters the double-blind treatment period) but fails to complete the double-blind treatment period will not be replaced. Measures will be taken to increase the recruitment rate, as needed, to ensure that a minimum of 330 patients (110 patients per treatment arm) are randomly assigned to treatment and 264 patients (up to approximately 88 patients per treatment arm) complete the double-blind treatment period and are evaluable for the primary efficacy analysis.

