#### **2.2.4. Safety Measures and Endpoints**

The safety of TV-45070 (4% and 8% ointment) will be assessed throughout the study by evaluating AEs, clinical safety laboratory test results, vital signs measurements, ECG findings, physical examination results, dermal irritation findings and concomitant medication usage. Skin rashes or skin irritation in the area of ointment application will be evaluated using a dermal irritation scale (modified Draize scale) at day 1 (at 1 hour after application of study drug), week 2, week 4, and week 8 for follow-up.

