### **4.2. Specification of Baseline Values**

For efficacy variables based on the weekly average of the daily average NRS scores, baseline is defined as the weekly average over the 7 days before randomization (day -7 to day -1). For other efficacy variables the baseline value is the last non-missing assessment on or before the first dose date if no assessment time is available. Otherwise, the baseline value is defined as the last non-missing assessment before the first dose of study medication.

The baseline value for safety variables (i.e., clinical laboratory, vital signs, ECG, and physical examination) is defined as the last non-missing assessment on or before the first dose date if no assessment time is available. Otherwise, the baseline value is defined as the last non-missing assessment before the first dose of study medication.

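### The dermal irritation table has no worst-score summary, so the peak reaction of a patient who stops for a skin reaction can be missing from it

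*SAP*

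**What the plan says.** SAP 7.9 gives the time points as follows: "Dermal irritation will be evaluated at baseline, week 2, week 4, follow-up, and early termination using the scale below". It then plans the summary: "The frequency and percentage of patients falling into each scale at each visit and last visit will be descriptively summarized in the table". The output is Table 15.3.23, and Listing 16.2.8.15 holds the individual evaluations.

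SAP 4.5 sets the rule for by-visit tables: "the assessments at the scheduled visits will be summarized in the tables while all of the assessments including unscheduled visits will be listed". It sends ET data to the last-visit summary and defines last visit as the last post-baseline value observed up to the week 4 visit.

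On the time course of reactions, Protocol 1.4.1 says that "they more often occur after a delay of 2 to 3 weeks and resolve soon after cessation of dosing". On ET timing, Protocol 4.4 says "An ET visit should be conducted within 2 weeks after the last study drug administration" (Protocol 3.1 has the same limit), while Protocol 3.11.3.4 says "there will be an ET visit as soon as possible after the last study drug administration".

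SAP 2.2.4 names the dermal score as a safety measure "at day 1 (at 1 hour after application of study drug), week 2, week 4, and week 8 for follow-up". SAP Table 1 schedules it at visit 2, visit 3 (one hour after the first application), visits 4 and 5, follow-up and ET.

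**The concern.** Local skin reaction is a recognised risk of this ointment, and the dermal score is the only planned measure that grades it on a dermatological scale. By the protocol's own account a reaction tends to appear around or after visit 4 and to fade once dosing stops. Patients with the worst reactions are the likeliest to stop early and have no week 4 visit. The week 4 column would then mostly describe patients who tolerated the ointment, and the last-visit column would hold whatever was seen last.

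Elsewhere the SAP guards against this. SAP 7.7 summarises the worst post-baseline ECG finding. SAP 4.1 has summaries of potentially clinically significant values draw on scheduled, unscheduled and ET data alike. The dermal score has no equivalent. If peaks drop out unevenly, the comparison of active ointment with vehicle is blurred on a named safety and tolerability measure.

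**Working it through.** The plan states no figure to reproduce, so the check is mainly a trace of one patient through the rules.

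**Timing**
- First application is on day 1, so a delay of 2 to 3 weeks puts onset at about day 1 + 14 = 15 to day 1 + 21 = 22.
- Visit 4 is day 15 ± 1 and visit 5 is day 29. Typical onset is at or after visit 4 and before visit 5.
- Protocol 4.4 uses the example of a patient who stops on day 20 and has no visit 5. The latest ET day is 20 + 14 = 34, which is 5 days after the week 4 visit would have been.

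**What the table shows for that patient if the reaction began after visit 4**

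| Column | Score shown |
|---|---|
| Week 2 | Pre-reaction score |
| Week 4 | None |
| Last visit, if a day 34 ET score counts | Possibly healed |
| Last visit, if data stop at week 4 | Visit 4 score, pre-reaction |
| Any unscheduled score during the reaction | Listed only |

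SAP 4.5 leaves it open which last-visit reading applies, because it both includes ET data and stops at week 4. Neither reading gives the peak unless the ET visit is prompt.

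**How often an ET visit would come too late.** The documents give no time to resolution, so three values are assumed. Over whole-day ET lags of 0 to 14 days (15 possible lags), a reaction clearing in R days is gone at 15 − R of them:
- R = 3: 12 of 15
- R = 7: 8 of 15
- R = 14: 1 of 15

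These count possible lags and are not probabilities, since actual lags are unknown.

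**How many patients are exposed to this.** Protocol 1.3.2.2 reports that in the earlier PHN crossover study 5 patients stopped for local skin reactions on placebo and 2 on active; 62 of its 68 patients received active ointment. The placebo denominator is not stated, so a range of 62 to 68 is used.
- Active: 2/62 = 3.2%; × 110 = 3.5 per arm
- Placebo: 5/68 = 7.4%; × 110 = 8.1. With 62, 5/62 = 8.1%; × 110 = 8.9

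These are projected withdrawals for skin reactions. Only some would have a peak missing from the table.

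**The case against.** The best defence is that skin tolerability does not rest on this table. AEs by severity, AEs causing discontinuation (Table 15.3.8) and a Kaplan-Meier analysis of time to first application-site irritation (SAP 7.3, Table 15.3.24) capture these patients whatever their visit dates. Protocol 4.4 also asks for a full final evaluation at withdrawal, a prompt ET visit would score the reaction, and one already present at week 2 stays in that column. All of this stands and limits the point to the score table. It does not replace a worst score. AE severity is graded by limitation of usual activities (Protocol 7.1.3), the Kaplan-Meier analysis gives timing and not peak severity, and none of its five preferred terms names vesicles, which are score 6 on the dermal scale.

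The two ET wordings can also be read together, as a target and an outer limit. That is fair, but the protocol does not say so.

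A reader might infer four stronger claims that the documents do not support:
- *The day 1 one-hour score goes unreported.* SAP 7.9 leaves it out of its list of time points, but visit 3 is a scheduled visit, the table covers each visit, and all assessments are listed. What is supported is an inconsistency with SAP 2.2.4 and SAP Table 1.
- *The day 1 post-dose score becomes the baseline.* SAP 4.2 says the safety baseline "is defined as the last non-missing assessment on or before the first dose date if no assessment time is available", but the variables it names are laboratory tests, vital signs, ECG and physical examination, not dermal scores. No dermal change from baseline is planned either.
- *The gap favours the drug.* Skin withdrawals in the earlier study were more frequent on placebo, so missed peaks could equally make the active arms look relatively worse.
- *About 15 peaks will be lost* (8 placebo plus 2 × 3.5 = 7 active). That is a count of projected withdrawals. It also borrows rates from a 3-week study of the 8% ointment only, applied at 7.5 rather than 3 µL/cm² (Protocol 1.5.1).

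**Conclusion.** The point holds for the dermal score table. As planned, Table 15.3.23 can omit the peak score of a patient who stops for a skin reaction and show a healed or pre-reaction score instead. It can understate peak irritation in whichever arm loses more patients this way, and the direction cannot be presumed. On the earlier study's rates, about 8 to 9 placebo patients and 3 to 4 per active arm are at risk of this. How many peaks would be lost depends on ET lag and time to resolution, which the documents do not give.

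No efficacy result is touched, and AE reporting still shows that these reactions occurred. The change is nonetheless worth making: a worst-score summary is a better description of a named safety measure, the SAP already does the equivalent for ECG, and it uses scores already due to be collected. The unnamed day 1 time point and undefined dermal baseline are minor clarifications.

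**What to change.** In SAP 7.9 and Table 15.3.23:
1. Add each patient's worst dermal score after the first dose, taken from all scheduled, unscheduled and ET assessments, as counts and percentages by arm.
2. Name the day 1 one-hour score as a post-dose column, in line with SAP 2.2.4 and SAP Table 1.
3. Label the visit 2 score as the dermal baseline.

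In the protocol, reconcile the ET timing in 3.11.3.4 with that in 3.1 and 4.4, so that sites and programmers work from one statement.

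The SAP change costs one extra row and one extra column in a descriptive table and needs no new data. It should be made before unblinding. The protocol change is to wording only. One limit remains: a worst-score row cannot recover a reaction that nobody scored while it was present.
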